#### 5.10.2.4. Analysis of Body Weight

Analysis of body weight based on MMRM will be summarized by treatment group using FAS.

#### 5.11. Insulin Dose

For the analysis of insulin dose, only descriptive statistics will be provided.

Daily insulin dose (unit and unit/kg body weight) for each insulin regimen (i.e. basal insulin, premixed insulin, or basal/mealtime insulin) at the baseline and specific time point (i.e. Visit 7 and Visit 12), and change from baseline will be summarized and listed using FAS.

For the patients using basal/mealtime insulin, daily insulin dose (unit and unit/kg body weight) for each insulin type (i.e. basal or mealtime insulin) at the baseline and specific time point (i.e. Visit 7 and Visit 12), and change from baseline will be summarized using FAS

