**Table GBGF.4.1. Objectives and Endpoints**

Objectives	Endpoints

Primary To show superiority of the addition of once-weekly dulaglutide 0.75 mg compared to the addition of once-weekly placebo to insulin treatment with or without 1 or 2 OADs, on change from baseline in HbA1c after 16 weeks of treatment in Japanese patients with T2D.
	
 
• The change in HbA1c from baseline to 16 weeks
 

Secondary For efficacy, to compare dulaglutide 0.75 mg to placebo at 16 weeks.
 
For safety, to compare dulaglutide 0.75 mg to placebo for 16 weeks.
 
To describe long-term efficacy of dulaglutide 0.75 mg in combination with insulin therapy up to 52 weeks.
 
To describe long-term safety of dulaglutide 0.75 mg in combination with insulin therapy up to 56 weeks (to include the follow-up period).
	
 
• Percentage of patients achieving HbA1c target values of <7.0% or ≤6.5% at 16 weeks
 
• The change in FSG (central laboratory) from baseline to 16 weeks
 
• The change in PG from 7-point SMPG profiles from baseline to 16 weeks
 
• The change in body weight from baseline to 16 weeks
 
• The change in insulin dose from baseline to 16 weeks
 
• TEAEs
 
• Incidence and rate of hypoglycemic episodes
 
• Adjudicated cardiovascular and pancreatic AEs
 
• Thyroid neoplasm AEs
 
• Allergic/hypersensitivity AEs
 
• Laboratory parameters of hematological safety and biochemical abnormalities
 
• Efficacy parameters described above
 
• Safety parameters described above
 

Exploratory Exploratory objectives are to assess the health outcomes variables at 16 and 52 weeks.
	
 
• Diabetes Treatment Satisfaction Questionnaire status (DTSQs)
 
• Diabetes Therapy Related Quality of Life (DTR-QOL)
 
• Device Questionnaire
 
• Dietary Evaluation
 

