#### **7.2.1.2. Insulin Treatment**

During the screening period, eligible patients on DPP-4 inhibitor, SU, or glinide will begin a 12-week washout of those medications; these patients may uptitrate their insulin dose for up to 4 weeks, followed by an 8-week stabilization ( $\pm 20\%$  adjustment) of insulin dose prior to Visit 3. For the patients who do not need to wash out, the insulin dose will remain unchanged during the screening and lead-in period.

After completion of the screening and lead-in period, the insulin dose at randomization will be fixed for the 16-week primary treatment period, except for patients who experience repeated or severe hypoglycemia (Section 7.4.1.2). During the 36-week extension treatment period in which all patients will be on dulaglutide and insulin therapy, the investigator will adjust the patient's insulin dose to achieve target blood glucose values (Table GBGF.7.2).

During the whole study period (16-week primary treatment period and 36-week extension treatment period), if repeated hypoglycemia (SMPG  $\leq 70$  mg/dL or symptomatic hypoglycemia) occurs, and it is considered to be related to the pharmacological therapy, the investigator can decrease the dose of insulin any time. If at least 1 episode meets the criteria for severe hypoglycemia (events requiring assistance to administer therapy) or is associated with SMPG  $< 54$  mg/dL recorded during the assessment period, the investigator should decrease the dose of insulin.

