#### 9.1.2. Secondary Efficacy Assessments

The following secondary efficacy measures will be evaluated at 16 and 52 weeks:

- Change from baseline in HbA1c (52 weeks)
- Percentage of patients achieving HbA1c targets of  $<7.0\%$  or  $\leq 6.5\%$ , as measured at the central laboratory
- Changes from baseline in FSG measured at the central laboratory
- Changes from baseline in PG from 7-point SMPG profiles
- Changes from baseline in body weight
- Changes from baseline in insulin dose

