#### **10.3.3.2. Secondary Analyses**

The primary analysis model, MMRM, will be repeated using the PP population to check the sensitivity of the analysis. If the conclusion differs from that of the FAS, the data and analyses will be further investigated. The secondary analysis for the primary endpoint will be an ANCOVA for HbA1c change from baseline to the Week 16 endpoint with treatment, and insulin regimen (basal insulin, premixed insulin, or basal/mealtime insulin) as fixed effects and baseline HbA1c as a covariate, with missing endpoints imputed with LOCF using postbaseline data only.

All secondary efficacy measures that are continuous variables (changes from baseline) other than HbA1c will be analyzed using MMRM on the FAS. There will be no multiplicity adjustment for pairwise treatment comparisons. The MMRM and ANCOVA models will include treatment, baseline HbA1c ( $<8.5\%$ ,  $\geq 8.5\%$ ), and insulin regimen (basal insulin, premixed insulin, or basal/mealtime insulin) as fixed effects and a covariate of baseline value.

Repeated measures logistic regression with generalized linear mixed model will be used to analyze for percentage of patients achieving HbA1c targets of  $<7.0\%$  or  $\leq 6.5\%$ .

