#### 5.10.2. Secondary Efficacy Analysis

Secondary efficacy measures that are continuous variables (changes from baseline) other than HbA1c will be analyzed using MMRM on the FAS. The MMRM model will include treatment, baseline HbA1c (<8.5%,  $\geq8.5\%$ ), and insulin regimen (basal insulin, premixed insulin, or basal/mealtime insulin) as fixed effects and a covariate of baseline value. Also, the ANCOVA models will include treatment, baseline HbA1c (<8.5%,  $\geq8.5\%$ ), and insulin regimen (basal insulin, premixed insulin, or basal/mealtime insulin) as fixed effects and a covariate of baseline value.

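### Change in insulin dose at Week 16 is a secondary endpoint for comparing dulaglutide with placebo, but the SAP plans no between-arm difference or confidence interval for it

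*SAP*

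**What the plan says.** Protocol Table GBGF.4.1 lists "The change in insulin dose from baseline to 16 weeks" among the secondary endpoints. The objective it serves is worded "For efficacy, to compare dulaglutide 0.75 mg to placebo at 16 weeks", and SAP 4.2 repeats that objective. Protocol 9.1.2 names the measure again among the secondary efficacy measures to be evaluated at 16 and 52 weeks: "Changes from baseline in insulin dose".

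Protocol 10.3.3.2 assigns the method: "All secondary efficacy measures that are continuous variables (changes from baseline) other than HbA1c will be analyzed using MMRM on the FAS". Protocol 10.3.1 adds that treatment comparisons are shown as a difference in least-squares means with its 95% CI and p-value.

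SAP 5.10.2 carries a near-identical general rule: "Secondary efficacy measures that are continuous variables (changes from baseline) other than HbA1c will be analyzed using MMRM on the FAS". Its subsections cover the HbA1c targets, fasting serum glucose, the 7-point glucose profile and body weight, but not insulin dose. That is handled in SAP 5.11, which opens "For the analysis of insulin dose, only descriptive statistics will be provided" and continues "Daily insulin dose (unit and unit/kg body weight) for each insulin regimen (i.e. basal insulin, premixed insulin, or basal/mealtime insulin) at the baseline", at Visit 7 and at Visit 12, with a further split by insulin type for basal/mealtime users. SAP 5.11 names no model, treatment difference, interval or all-regimen total.

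On dosing, Protocol 7.2.1.2 fixes insulin for the 16-week period with an exception for hypoglycemia. For repeated hypoglycemia judged related to drug therapy, "the investigator can decrease the dose of insulin any time". For a severe episode, or one with a self-monitored value below 54 mg/dL, it says the dose should be decreased.

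**The concern.** An endpoint that the protocol sets up for comparison reaches the SAP without a comparison. If SAP 5.11 is followed as written, the report will contain no pre-specified estimate of how far the arms differ in change in insulin dose, and no statement of its uncertainty.

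The quantity matters for interpretation. Protocol 5.4 holds insulin fixed so that the 16-week contrast reflects dulaglutide alone. The dose can still come down when hypoglycemia occurs, and hypoglycemia may differ between arms. A larger reduction in one arm would bear on how both the HbA1c and the hypoglycemia differences are read. A between-arm estimate of dose change is the direct check on the fixed-dose premise.

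The treatment is also uneven. SAP Version 3 added analysis of covariance (ANCOVA) comparisons with 95% CIs and p-values for the DTSQs and DTR-QOL (SAP 5.12.1 and 5.12.2), which the protocol classes as exploratory. A named secondary endpoint has no counterpart.

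**Working it through.** **Comparison of the texts**
- Objective: compare the arms at 16 weeks (Protocol Table GBGF.4.1; SAP 4.2).
- Endpoint under that objective: change in insulin dose (Protocol Table GBGF.4.1 and 9.1.2).
- Method in the protocol: MMRM on the full analysis set (10.3.3.2).
- Method in the SAP: descriptive only (5.11). This specific statement governs over the general sentence in 5.10.2, which unlike the protocol sentence does not begin with the word *all*.
- Reason for the change: none in SAP 5.11 or in the revision history (SAP 3).

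**The plan's own figure**

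The only stated precision is for HbA1c (Protocol 10.1; SAP 5.1): difference 1.0, SD 1.0, 102 v 34 completers, two-sided alpha 0.05.
- Completers: 120 × 0.85 = 102; 40 × 0.85 = 34.
- Standard error: 1.0 × √(1/102 + 1/34) = 0.198.
- Power: Φ(1.0/0.198 − 1.96) = Φ(3.09) = 0.999.

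The stated power of more than 99% is reproduced. Nothing comparable is given for insulin dose.

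**Precision for insulin dose, in SD units**

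Expected regimen sizes follow from the 60/20/20 enrollment targets (Protocol 5.1) and 3:1 allocation of 160 patients:
- Basal: 160 × 0.60 = 96, or 72 v 24.
- Premixed, and likewise basal/mealtime: 160 × 0.20 = 32, or 24 v 8.

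The 95% half-width is t(0.975; n₁ + n₀ − 2) × SD × √(1/n₁ + 1/n₀).

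| Comparison | n | Calculation | Half-width |
|---|---|---|---|
| Pooled, completers | 102 v 34 | 1.978 × 0.198 | 0.39 SD |
| Pooled, randomized | 120 v 40 | 1.975 × 0.183 | 0.36 SD |
| Basal, randomized | 72 v 24 | 1.986 × 0.236 | 0.47 SD |
| Premixed or basal/mealtime, randomized | 24 v 8 | 2.042 × 0.408 | 0.83 SD |

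Like for like on randomized numbers, the basal interval is 0.468/0.361 = 1.3 times as wide as the pooled one, and the smaller regimens 0.834/0.361 = 2.3 times.

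**In units of insulin**

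The SD of the change has to be assumed. At 1, 3 and 5 units, the pooled completer half-width is 0.392 × 1 = 0.4, 0.392 × 3 = 1.2 and 0.392 × 5 = 2.0 units. These figures assume one common SD and roughly normal changes. Neither is likely to hold well, so they indicate scale only.

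**The case against.** The strongest defense is the design itself. Insulin is fixed for 16 weeks and only hypoglycemia-driven reductions are foreseen, so most changes should be zero and the rest negative. A normal-theory MMRM would suit such data poorly. SAP 5.11 also uses only Visit 7 within the blinded period, so with a single post-baseline value the model would reduce to an ANCOVA. This stands as an argument against restoring the protocol's model unchanged. It does not remove the need for an estimate, and neither document gives it as the reason.

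Reporting by regimen is also defensible. Protocol Section 3 cites average doses of 10 to 15 IU for basal insulin and 40 to 50 IU for basal/mealtime insulin, so changes in units are on different scales. The by-regimen tables should stay, but they cannot replace a pooled comparison.

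Both documents allow a non-principal change of method to be justified in the clinical study report (Protocol 10.3.1; SAP 5.2), so the missing reason is not in itself a breach.

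Two stronger readings are tempting and are not supported.
- A reader might infer that nothing by arm will be shown. SAP Table GBGF 5.1 sets placebo, dulaglutide and total as the display groups for the double-blind period, so by-arm columns are likely even though 5.11 does not name treatment group. A reader could then form a crude difference. The exact layout is in a separate list of analyses.
- A reader might infer that the comparison was dropped late or after results were seen. SAP Version 1 was approved before the first patient visit, and the changes listed for Versions 2 and 3 do not mention insulin dose.

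**Conclusion.** The mismatch is explicit in the text and needs no assumption. The protocol calls for a between-arm comparison of change in insulin dose at Week 16, and the SAP plans description only, with no pre-specified difference or confidence interval and no stated reason.

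The practical weight is minor. The primary HbA1c analysis does not use insulin dose, secondary endpoints carry no multiplicity control, and by-arm summaries will probably appear. What is lost is a ready check on whether insulin reductions differed between arms.

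A pooled estimate is feasible, with a half-width of about 0.39 SD among completers, against roughly 0.47 to 0.83 SD within single regimens on randomized numbers. Those figures rest on the planned enrollment mix, 15% dropout and normal theory. Their value in units depends on an SD that the documents do not give.

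**What to change.** In SAP 5.11, keep the by-regimen tables, state that they are by treatment group, and add:
- The Week 16 dulaglutide-minus-placebo difference in change in daily insulin dose, in units, with a 95% CI, pooled over regimens and adjusted for insulin regimen and baseline dose.
- A rank-based or bootstrap interval in place of the normal-theory one, because many changes will be zero. With mostly tied zeros a rank-based shift estimate can itself be zero, so a bootstrap interval for the adjusted mean difference may be more informative. Name the choice in advance.
- The percentage of patients with any dose reduction from baseline to Week 16, by arm, as a supportive summary.
- If units/kg is also compared, division by baseline weight at both time points. With current weight, weight loss at an unchanged dose changes the ratio and could create a difference between arms that is not a dose difference.

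Add one sentence explaining why this replaces the MMRM of Protocol 10.3.3.2, and repeat it in the clinical study report. If the sponsor prefers description only, both documents should say so and give the reason.

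The cost is one extra table. Visit 7 doses are already to be summarized, so no new data are needed.

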## 5.12. Health Outcome Analyses

## 5.12.1. DTSQs (Diabetes Treatment Satisfaction Questionnaire status)

Summary statistics for each dimension and total score by visit and change from baseline values will be provided using FAS. Hyperglycemia, hypoglycemia, total score except blood glucose control score and total score at Week 16 will be compared between treatment groups using an ANCOVA models that includes treatment and insulin regimen (basal insulin, premixed insulin, or basal/mealtime insulin) as fixed effects and a covariate of baseline value. The LS means and 95% confidence intervals for treatment difference and p-values for comparisons will be reported.

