### Statistical Analysis:

The primary analysis model will be mixed-model repeated measure (MMRM) analysis using restricted maximum likelihood with treatment, insulin regimen (basal insulin, premixed insulin, or basal/mealtime insulin), visit, and treatment-by-visit as fixed effects, a covariate of baseline value, and patient as a random effect. For analyses of variables other than HbA1c, the HbA1c stratum (<8.5%, ≥8.5%) will be included in the model. An unstructured covariance structure will be used to model the within-patient variability and implicitly adjust for missing data. The secondary analysis for the primary endpoint will be analysis of covariance using a similar model as described above with treatment, and insulin regimen (basal insulin, premixed insulin, or basal/mealtime insulin) as fixed effects and baseline HbA1c as a covariate, with missing endpoints imputed with the last (postbaseline) observation carried forward. All secondary efficacy measures that are continuous variables (changes from baseline) will be analyzed using MMRM. Repeated measures logistic regression with generalized linear mixed model will be used to analyze for percentage of patients achieving HbA1c targets of <7.0% or ≤6.5%. Analyses for other secondary efficacy categorical measurements will use the repeated measures logistic regression with generalized linear mixed model, unless otherwise noted.

The primary analysis population will be the full analysis set, defined as all patients who received at least 1 dose of study treatment and have at least 1 measurement of HbA1c after study treatment. The safety population will include all patients who received at least 1 dose of study treatment. The primary efficacy measure (HbA1c) will also be evaluated in the Per-Protocol population.

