## 3. Revision History

SAP Version 1 was approved prior to First Patient Visit (FPV).

SAP Version 2: Unblinding Plan Section was added to clarify the unblinding plan and blinding strategy throughout the study conduct. Summary of concomitant medication and plot of SMPG during follow-up period have been added.

SAP Version 3: Some post hoc analyses were added: Statistical tests were added for DTSQs and DTR-QOL.

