## 5. A Priori Statistical Methods

## 5.1. Determination of Sample Size

A total of approximately 160 patients (dulaglutide: 120 patients; placebo: 40 patients) will be randomized to have approximately 136 completers (dulaglutide : 102 patients; placebo: 34 patients) to show dulaglutide is superior to placebo with more than 99% power assuming a treatment difference of 1.0% in HbA1c reduction, standard deviation (SD) = 1.0%, and dropout rate of 15%. The screen failure rate is estimated as 20%. Approximately 200 patients will be screened.

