#### 5.2.1. Analysis Populations

The analysis populations used in the study are described below (Table GBGF 5.2).

Population	Definition	
All Entered	All patients who signed informed consents	
All Randomized	All patients who were randomized to a treatment arm	
Non-randomized	All patients entered but not randomized to a treatment arm	
Full Analysis Set (FAS)	All patients who received at least one dose of study treatment and have at least one measurement of HbA1c after study treatment	
Per-Protocol Set (PPS)	All patients in the FAS who meet the following criteria:	
	• Have no important protocol deviations that could impact the assessment of the primary objective (see section 5.4)	
	• At least 75% compliant with the required doses of investigational product	
	• Complete the treatment period (16 weeks [Visit 7]) for primary endpoint	
	• Not missing more than 2 consecutive weekly injections of investigational product or more than 14 consecutive daily injections of insulin	
Safety Analysis Set	All patients who received at least one dose of study treatment	

 Table GBGF 5.2.
 Analysis Population for Study H9X-JE-GBGF

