#### 5.10.2.3. Analysis of 7-point SMPG profile

The 7-point SMPG profiles before and 2 hours after breakfast, before and 2 hours after lunch, before and 2 hours after dinner, and bedtime will be obtained within 2 weeks prior to corresponding visit. In general, the mean of the two daily mean values will be used for reporting purpose. If the value from either day is missing, then the non-missing value will be used as the mean of the two daily mean values. Also, if both two daily mean values are missing then the mean of the two daily mean values will be missing. The daily mean is calculated as the mean of available values collected on a particular day.

The following variables for 7-point SMPG profile will be analyzed using ANCOVA model with missing endpoints imputed with LOCF:

- 1. Pre morning meal PG (mg/dL)
- 2. 2-hour postprandial measurement for morning meal PG (mg/dL)
- 3. Pre midday meal PG (mg/dL)
- 4. 2-hour postprandial measurement for midday meal PG (mg/dL)
- 5. Pre evening meal PG (mg/dL)
- 6. 2-hour postprandial measurement for evening meals PG (mg/dL)
- 7. Bedtime BG (mg/dL)
- 8. Morning meal 2-hr excursion (mg/dL)
- 9. Midday meal 2-hr excursion (mg/dL)
- 10. Evening meal 2-hr excursion (mg/dL)
- 11. Mean of all meals 2-hr excursion
- 12. Mean of all 7-point PG (mg/dL)
- 13. Mean of all pre-meals PG (mg/dL)
- 14. Mean of all postprandial meals PG (mg/dL)
- 15. Circadian variation in 7-point PG (mg/dL)

For before and 2 hours after meal, and bedtime PG (reports 1-7), the mean PG value at each visit is calculated as the average of 2 daily PG values. The change from baseline is calculated as the mean PG value at endpoint minus the mean PG value at the baseline.

For the morning, midday and evening meal 2-hr excursion (reports 8-10), the daily excursion for each meal is calculated as the postprandial meals PG minus the fasting plasma glucose (FPG). The mean glucose excursion for each meal at each visit is calculated as the average of 2 daily glucose excursions. The change from baseline is calculated as the mean excursion at endpoint minus the mean excursion at baseline.

For mean of all meals 2-hr excursion at each visit (report 11), the daily mean for all meals is calculated as the average of glucose excursion for morning, midday and evening meals on a particular day. The mean of all meals 2-hr excursion at each visit is calculated as the average of 2

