## 5.12.2. DTR-QOL (Diabetes Therapy Related-Quality of Life)

Summary statistics for each dimension and total score by visit and change from baseline values will be provided using FAS. Each dimension and total score at Week 16 will be compared between treatment groups using an ANCOVA models that includes treatment and insulin regimen (basal insulin, premixed insulin, or basal/mealtime insulin) as fixed effects and a covariate of baseline value. The LS means and 95% confidence intervals for treatment difference and p-values for comparisons will be reported.

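### The Week 16 DTSQs and DTR-QOL models omit the HbA1c randomization stratum and give no rule for patients who leave before Week 16

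*SAP*

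**What the plan says.** **The tests.** SAP 5.12.1 compares four DTSQs scores at Week 16: hyperglycemia, hypoglycemia, and the total with and without the blood glucose control score. The "total score at Week 16 will be compared between treatment groups using an ANCOVA models that includes treatment and insulin regimen", with the baseline score as covariate. SAP 5.12.2 does the same for DTR-QOL: "Each dimension and total score at Week 16 will be compared between treatment groups using an ANCOVA models", with the same terms. SAP Section 3 records when they came in: "Some post hoc analyses were added: Statistical tests were added for DTSQs and DTR-QOL".

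**The stratum.** Protocol 7.2 stratifies randomization by insulin regimen and by Visit 2 HbA1c (<8.5%, ≥8.5%). The synopsis has a sentence that opens "For analyses of variables other than HbA1c, the HbA1c stratum" and places that stratum in the model. Protocol 10.3.3.2 and SAP 5.10.2 carry it, beside the regimen, in the MMRM and ANCOVA models for secondary efficacy.

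**Patients who leave.** Protocol 8.1 and 8.2 require a patient who stops study drug to leave the study. Protocol 8.1.1 has that patient complete the ET visit unless consent is withdrawn. The Schedule of Activities marks both questionnaires at Weeks 0, 16 and 52 and at ET. SAP 5.12 mentions neither ET nor missing scores. For the 7-point SMPG profile, SAP 5.10.2.3 does give a rule: the variables "will be analyzed using ANCOVA model with missing endpoints imputed with LOCF".

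**The concern.** A factor that governed the randomization would normally be in the model that tests the randomized comparison. Here one of the two factors is kept and the other is left out without comment. If HbA1c stratum predicts satisfaction or treatment-related quality of life beyond the baseline score, its variation stays in the residual. The comparison then loses precision, and the standard error no longer reflects the way patients were allocated.

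The second gap concerns who is compared. A patient who leaves before Week 16 has an ET questionnaire and no Visit 7 questionnaire. With no rule, an analyst could either exclude that patient or carry the ET score forward, and both would be consistent with the text. The choice could then be made after the data are seen. If the patient is excluded, collected data go unused in the comparison.

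**Working it through.** **1. Where HbA1c enters each model**

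| Model | Insulin regimen | HbA1c term |
|---|---|---|
| Randomization (protocol 7.2) | yes | stratum, Visit 2 |
| HbA1c MMRM and ANCOVA (SAP 5.10.1) | yes | continuous baseline HbA1c |
| HbA1c targets (SAP 5.10.2.1) | yes | continuous baseline HbA1c |
| Other continuous secondary measures (SAP 5.10.2) | yes | stratum |
| DTSQs, DTR-QOL (SAP 5.12.1, 5.12.2) | yes | none |

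In the HbA1c models the continuous baseline value does the work of the stratum. In the questionnaire models the baseline covariate is the questionnaire score, so nothing represents HbA1c.

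Let R² be the share of residual variance that the stratum would explain, given baseline score and regimen. The standard error with the stratum is then about √(1 − R²) times the standard error without it. The documents give no R², so no number follows. The price of adding the term is one degree of freedom. With 136 patients and five parameters (intercept 1, treatment 1, regimen 2, baseline 1), residual degrees of freedom go from 136 − 5 = 131 to 130.

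**2. How many patients the missing rule could touch**

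The plan's own figures reproduce:
- 160 × 0.85 = 136; 120 × 0.85 = 102; 40 × 0.85 = 34.
- HbA1c power: SE = √(1/102 + 1/34) = 0.198 for SD 1.0; 1.0/0.198 − 1.96 = 3.09; Φ(3.09) = 0.999, which agrees with the stated figure of more than 99%.

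The documents give no effect size, SD or power for either questionnaire.

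Patients who might lack a Week 16 score: 160 − 136 = 24 (18 dulaglutide, 6 placebo). This is an upper bound. Protocol 5.2 describes the 136 as completing the study, and patients who leave after Week 16 already have a Visit 7 score. If all 24 supplied an ET score, the SE of the difference would go from √(1/102 + 1/34) = 0.198 SD to √(1/120 + 1/40) = 0.183 SD.

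**3. What exclusion could do to the comparison**

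Let d be the share of an arm that leaves before Week 16, and g the amount, in SD, by which its leavers score worse than its stayers. Among stayers only, the difference is shifted toward dulaglutide by

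d(dulaglutide) × g(dulaglutide) − d(placebo) × g(placebo).

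All values of g below are assumptions:
- Equal d and equal g: 0.15 × 1 − 0.15 × 1 = 0.
- d = 0.15 in both arms, only dulaglutide leavers 1 SD worse: +0.15 SD, toward dulaglutide.
- d = 0.15 in both arms, only placebo leavers 1 SD worse: −0.15 SD, toward placebo.
- d = 0.05 in both arms, 1 SD gap in one arm only: 0.05 SD in either direction.

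The documents fix neither the sign nor the size.

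**4. The nearest comparator**

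Through Week 16, SMPG profiles are collected at the same points as the questionnaires: Week 0, Week 16, and ET for patients who leave before Week 16. The ET profile is therefore the only postbaseline value that LOCF could carry to Week 16 for such a patient. The SAP thus already uses ET data for an outcome collected in the same way.

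**The case against.** **The SAP does not say completers only.** Correct. For the summaries it says "Summary statistics for each dimension and total score by visit and change from baseline values will be provided using FAS", and the FAS is "All patients who received at least one dose of study treatment and have at least one measurement of HbA1c after study treatment", so it can include early leavers. Protocol 10.3.1 has a general-looking LOCF sentence, and the ANCOVA in SAP 5.10.2 is itself specified without LOCF. A reader might infer that the tests are restricted to patients still in the study; the text does not establish that. What remains is that the protocol's LOCF sentence follows the ANCOVA for HbA1c and does not name health outcomes. An FAS member with no Week 16 score cannot enter a Week 16 ANCOVA unless a rule supplies one.

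**The stratum was meant for efficacy models.** The synopsis sentence sits within the efficacy model description, and protocol 10.3.5 plans only summary statistics for these questionnaires. SAP 5.12 therefore departs from no questionnaire model in the protocol. This stands as a point about wording. It does not explain why one stratification factor was kept and the other left out.

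**Leavers are the dissatisfied patients.** This is tempting, but no passage says so. The likely reasons for leaving may pull in opposite directions. Severe, persistent hyperglycemia (protocol 7.4.1.3) might be expected mainly on placebo, while the nausea and vomiting named in protocol 10.3.4.2 are tied to dulaglutide.

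**Post hoc tests presented as planned.** The tests sit under the Section 5 title "A Priori Statistical Methods", and a reader might add that nine tests (four DTSQs, five DTR-QOL) give 1 − 0.95⁹ = 0.37. That figure assumes independence, whereas the totals contain their own parts. The Revision History already calls the tests post hoc, protocol 10.3.1 discloses that multiplicity is not adjusted, and SAP 5.2 requires changes from protocol methods to be described in the study report. A label in 5.12 would be editorial.

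**Conclusion.** Two specification gaps hold. First, both Week 16 ANCOVAs omit the HbA1c stratum although it was a randomization factor and the comparable secondary-efficacy ANCOVAs include it. The omission does not invalidate the tests, since stratified allocation keeps the arms balanced on the stratum. The loss is in precision and consistency, and its size cannot be computed without the association between HbA1c stratum and the scores.

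Second, there is no rule for patients who leave before Week 16, despite their ET questionnaires. At most 24 patients are affected, on the assumption that all 15% dropout precedes Week 16. Bias in the comparison requires dropout, or the gap between leavers and stayers, to differ between arms. The illustrative shifts of up to 0.15 SD come from assumed gaps and should not be read as an estimate of bias, nor as favouring dulaglutide.

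The weight is modest: the objective is exploratory and the tests are recorded as post hoc.

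**What to change.** In SAP 5.12.1 and 5.12.2:

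1. Add the HbA1c stratum (<8.5%, ≥8.5%) as a fixed effect beside insulin regimen. State whether it is the Visit 2 value used at randomization or the baseline category named in SAP 5.10.2. Cost: one degree of freedom.
2. State that the main comparison uses scores observed at Week 16. Add a sensitivity analysis that takes the ET score as the Week 16 endpoint for patients who discontinue before Week 16, in line with LOCF for SMPG. Report the number of patients per arm in each analysis.
3. Optional and editorial: label the tests post hoc in 5.12.

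No new data are needed. The downside of item 2 is that ET scores come from different weeks and may be taken up to 14 days after the decision to discontinue. That is why the ET analysis is better placed as a sensitivity analysis than as the main one.
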